Game-based interventions have a well-established role in health promotion and behavior change. Games designed to educate, train, or change behavior as they entertain players (also known as "serious games"⁴⁵) have been shown to improve health outcomes in youth (e.g., smoking, depression, and anxiety).⁴⁶⁻⁷³ Serious games can also enhance players' emotional intelligence and mastering of coping strategies.⁷⁴⁻⁷⁶ Game-based interventions are unique in that they offer opportunities for simulated role play, a highly effective approach for situated learning.⁷⁷ Role play allows players to practice skills in an entertaining way^{78,79} and can influence healthy attitudes and behaviors.^{80,81} This "hands on" approach to learning allows for the acquisition and rehearsal of new skills that can then be transferred to real life situations.⁸² Serious games can create contextualized learning experiences that are meaningful to the player, which are known to create long-term retention of new knowledge and cognitive skills.⁸³ Other advantages of games include increased fidelity and cost-effectiveness.⁸⁴⁻⁹⁰ While the potential for game-based interventions are promising, there continues to be a great need for the development and rigorous testing of theory-driven game-based interventions.⁶³

Web-accessible game-based interventions can improve health among SGM populations and can overcome barriers associated with effectively reaching the growing population of SGMY. Game-based interventions with young men who have sex with men have improved HIV-related outcomes using choose-your-own adventure narratives to help them navigate barriers in a safe space.⁹¹⁻⁹³ Competition-based games using personalized normative feedback have reduced alcohol use among sexual minority adult women.⁹⁴ Also, game-based cognitive behavioral therapy components have taught sexual minority youth behavioral change skills to improve depression.⁹⁵ Web-based game interventions are also an effective way to reach large numbers of SGMY, including those living in rural and high structural stigma locations (i.e., areas with less SGM-inclusive policies, institutions, and attitudes), who may be insufficiently supported by face-to-face programs.^{96,97} Though web-accessible game interventions are effective and overcome common impediments of face-to-face interventions, there is a lack of games aimed at preventing and reducing SGMY alcohol use.

Discrimination, stigma, and minority stressors are primary contributors to SGMY alcohol use inequities. Stigma Theory^{98,99} posits that SGMY experience multiple forms of discrimination (related to their sexual or gender minority statuses) at multiple levels of the social ecological model. Such discrimination includes internalized stigma (i.e., when SGMY internalize negative stereotypes about themselves), interpersonal stigma (i.e., direct or enacted forms of verbal, physical, and sexual harassment because of one's sexual identity or gender,^{100,101} occurring in-person or online), and structural stigma (i.e., locales with fewer SGM-inclusive policies, institutions, and attitudes). Minority Stress^{102,103} posits that these multiple forms of discrimination lead SGMY to experience chronic and acute psychological distress, which in turn lead some to cope via alcohol use. Much empirical research, including our own, has confirmed these theories, and identified discrimination and minority stress as primary contributors of SGMY alcohol use inequities.¹⁰⁴⁻¹⁰⁹ Therefore, interventions for SGMY must aim to prevent discrimination and/or teach SGMY to cope with stress to efficaciously reduce their alcohol use. Such interventions may be particularly useful for SGMY who have multiple minoritized identities (e.g., racial/ethnic minority SGMY) because they face compounding intersectional stigma, discrimination, and stress.

Intervention efficacy for preventing and reducing alcohol use may be moderated by minority stressors. With sexual minority adults, 2 sexuality-affirming interventions had greater efficacy for reducing alcohol use among participants with higher levels of baseline internalized stigma.^{110,111} Said differently, higher internalized stigma was associated with greater treatment benefit for reducing alcohol. Authors speculated men with greater internalized stigma may use alcohol to cope with internalized negative beliefs, and through the intervention they learned alternative coping skills to decrease their drinking behaviors.^{110,111} To build on the rigor of prior research, this R01 will: (1) investigate, for the first time, minority stressors as moderators of intervention efficacy among SGMYs; (2) examine multiple minority stressors at multiple levels of the social ecological model, including structural stigma, interpersonal stigma, and racism; and (3) use mixed methods to quantify the moderating effects and triangulating these data with participant descriptions about why and how minority stress affects intervention efficacy. A mixed methods study investigating whether, how, and why minority stress moderates the impact of interventions for reducing SGMY alcohol use can inform the field about for whom SGMY-affirmative interventions are most beneficial and illuminate for whom additional interventions are needed.

Study Objectives

Aim 1. Test the efficacy of a game-based intervention for reducing alcohol-related harms among SGMY.

Aim 2. Describe how baseline minority stressors (across proximal and distal domains) affect intervention efficacy.

Study Design & Methods

This study is a randomized controlled trial with SGMY (n=1,992) who are recruited via social media from across the United States. Participants will be randomized after baseline to the Intervention or Control condition. We will conduct surveys with SGMY at baseline, 3-, 6-, and 12-month follow-up. All study procedures related to screening, consenting, and surveying will be completed using REDCap, a free and secure HIPAA-compliant website for managing Web-based longitudinal survey studies.

This study will test the efficacy of our game-based intervention, Singularities, for preventing and reducing SGMY alcohol-related harms (primary outcome) and other health risk behaviors. We will examine whether minority stressors at multiple levels of the social ecological moderate intervention efficacy.

Intervention Condition: Singularities

Singularities is a theory-based, community-informed, web-accessible, roleplaying game-based intervention incorporating primary components: reducing alcohol-related harms; fostering healthy identity development in a safe environment; encouraging help-seeking behaviors; encouraging use of productive coping; and encouraging healthy internet and social media use.

Control Condition: Food4Thought

We will compare Singularities against an attention control condition (ACC) in which we will provide participants with similar amounts of research team contact and program contact, but without the active ingredients of Singularities intervention, namely the educational content that aims to enhance SGMY's alcohol protective behavioral strategies, distress tolerance skills, emotional regulation strategies, and healthy social media usage. The ACC will be asked to play a game, titled Pick Your Plate! A Global Guide to Nutrition, developed by the Smithsonian Science Education Center. Participants are instructed to build healthy meals using cuisine from around the world while ensuring they stick to a budget and meet all their nutritional needs. Importantly, this game does not include alcohol. In addition, they will be provided with educational modules based on USDA's nutritional materials, including MyPlate, that teach teens about healthy nutrition. The game and educational modules will be similar in length to the Singularities game and website, but with a different health focus. After their completion in the RCT, we will provide the game at no cost to control participants.

Eligibility Criteria

Inclusion: Individuals will be eligible if they are comfortable participating in English, live in the U.S., are 14-18 years old, have a sexual minority identity (i.e., gay, lesbian, bisexual, or queer) or a gender minority identity (i.e., consider themselves to be transgender or nonbinary), have an internet-accessible computer, smart phone, or tablet, and provide an email address; have drank alcohol in their lifetime or intend to in the next year.

Exclusion: We exclude people who are cisgender heterosexuals.

Statistical Considerations

We will use StataSE. Type I error will be set at 5% for all analyses. We will examine whether baseline characteristics are associated with study arm. We will control for variables (potential confounders) that differ meaningfully across study arms and are prognostic with the outcome.

Our primary analyses will use generalized linear mixed models (i.e., multilevel repeated-measures models) with a random effect for observations nested within persons and a link function dependent on the outcome distribution. Using a parallel two-group design, we will test whether the Poisson event rate ratio ($\lambda_{\text{intervention}} / \lambda_{\text{control}}$) for alcohol-related harms reported at T2 (primary outcome) is different from 1. To examine whether there are greater improvements over time in the intervention versus control conditions, we will test the interaction term of time by condition. We will conduct our primary analyses as intent-to-treat, wherein all participants are included according to the condition they were randomized to (i.e., 1=intervention 0=control). Time will be categorical (T1, T2, T3, T4).

To explore how participants' pre-intervention minority stress levels and demographics moderate the intervention effects on outcomes (e.g., how outcomes differ across subgroups), we will use similar modeling techniques to those used above with some exceptions. Our primary effects of interest in Aim 2 are the 3-way interactions between time × study arm × potential effect modifiers. These multivariable models will contain the 3-way interaction term, all 2-way interaction terms, main effects of time, study arm, potential effect modifier, and any variables that meaningfully differ between study arms at baseline. We will conduct both intent-to-treat and intensity-adjusted analyses. A significant 3-way interaction suggests the presence of intervention effect heterogeneity; we will follow the approach of Kraemer^{112,113} by focusing on effect size derivation rather than formal hypothesis testing. We will use Stata's postestimation "margins" command to probe the 3-way interaction terms to provide simpler meaningful results.

References

3. Institute of Medicine. *The health of lesbian, gay, bisexual, and transgender people: Building a foundation for better understanding*. National Academies Press; 2011.

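### Covariates enter the primary model only if they look imbalanced between randomised arms, which forgoes most of the available precision for the T2 rate ratio and leaves the model open to choice

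*Combined protocol and SAP*

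**What the plan says.** Statistical Considerations first announces a comparison of the arms at baseline: "We will examine whether baseline characteristics are associated with study arm". It then gives the adjustment rule: "We will control for variables (potential confounders) that differ meaningfully across study arms and are prognostic with the outcome". A variable must therefore pass two conditions, imbalance and prognosis. The plan gives no list of variables, no cut-off for either condition, no decision-maker and no time at which the choice is made.

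The primary-analysis paragraph adds no fixed covariates. It specifies a generalised linear mixed model with a person-level random effect. Baseline is one of the repeated measures: "Time will be categorical (T1, T2, T3, T4". The primary test is whether the rate ratio "for alcohol-related harms reported at T2 (primary outcome) is different from 1". For improvement over time, "we will test the interaction term of time by condition".

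The Aim 2 paragraph has a different rule. Its models include "any variables that meaningfully differ between study arms at baseline", with no prognostic condition. On error control the plan says only "Type I error will be set at 5% for all analyses".

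**The concern.** Study Design & Methods states that randomisation follows the baseline survey, so any baseline difference between arms arises by chance. Calling imbalanced variables confounders carries observational reasoning into a randomised design. What matters for precision is whether a variable predicts the outcome, not whether it happens to differ between arms.

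Two things are at stake. First, a prognostic variable is omitted whenever it is balanced, which is the usual case, and the precision it could give the T2 rate ratio goes with it. Second, the primary model is not fixed in advance. The word *meaningfully* has no definition, and the plan does not say on which data a variable would be judged prognostic. Several versions of the model would be defensible once arm data are available.

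**Working it through.** **Inputs.** From the documents: N = 1,992; 5% type I error; a two-sided question (rate ratio different from 1); T1 to T4 as response times. Assumed, because the documents do not give them: 1:1 allocation (996 per arm), the covariate–outcome correlation ρ, the number of candidate covariates k, and the imbalance cut-off. N = 1,992 cannot be reproduced, because no power, effect size, event rate, dispersion or dropout is stated. The point does not depend on it.

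**1. How much the undefined word decides.** With k independent candidates, each flagged with probability p, the chance of at least one flag is 1 − (1 − p)^k. A standardised mean difference (SMD) has standard error √(2/996) = 0.0448. Hence p = 0.026 for |SMD| > 0.1 and p = 0.265 for |SMD| > 0.05.

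| Cut-off | k = 5 | k = 10 | k = 20 |
|---|---|---|---|
| p < 0.05 | 23% | 40% | 64% |
| p < 0.10 | 41% | 65% | 88% |
| SMD above 0.1 | 12% | 23% | 41% |
| SMD above 0.05 | 79% | 95% | 100% |

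These are chances of a flag. For Aim 1 a flagged variable must also be judged prognostic, so the chance of actual adjustment is lower.

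**2. Precision of the T2 contrast.** Use a linear approximation and set the unadjusted variance to 1. Write Z for the standardised chance imbalance in the covariate.

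- Fixed adjustment: variance 1 − ρ².
- Adjust only if |Z| > 1.96: variance (1 − ρ²) + ρ² × E[Z²; |Z| ≤ 1.96]. The expectation is 0.95 − 2 × 1.96 × 0.0584 = 0.721. The reduction is therefore 0.279ρ², a little over a quarter of what fixed adjustment gives.

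| Assumed ρ | Reduction, fixed | Reduction, imbalance rule |
|---|---|---|
| 0.30 | 9.0% | 2.5% |
| 0.41 | 16.8% | 4.7% |
| 0.55 | 30.3% | 8.4% |

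Simulation at 996 per arm gave about 9%, 16% and 29% against 2%, 4% and 9%, which agrees within simulation error.

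In power terms, suppose the unadjusted T2 contrast had 80% power (assumed). Fixed adjustment gives Φ(2.80/√(1 − ρ²) − 1.96), which is 84%, 87% and 92% for the three correlations. In a simulation with R² = 0.30, power was 78–81% unadjusted, 80–83% under the imbalance rule and 91–93% with fixed adjustment.

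A simulation of overdispersed counts at T1 and T2 points the same way. The variance of the T2 log rate ratio fell by 10% with one moderate covariate and by 33% with the baseline outcome as covariate.

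**3. The interaction.** Let D1 and D2 be the arm differences at T1 and T2, DX the arm difference in the covariate, and g its coefficient. Adjustment gives (D2 − g·DX) − (D1 − g·DX) = D2 − D1, so the covariate cancels. In the count simulation with complete data the interaction estimate changed by less than 1e-14.

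**4. Type I error.** Applied mechanically at p < 0.05, the rule gave simulated error of 3.3–5.0%. Taking the most favourable of four versions (no adjustment, p < 0.05, |SMD| > 0.1, |SMD| > 0.05) gave 5.5–7.4%.

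**5. Baseline harms used twice.** T1 harms is already a response row. If it is also a covariate in a linear random-intercept model with T1 and T2 rows, its coefficient is pulled to g = (1 + ρ)/2 and the T2 variance is 1 + g² − 2gρ.

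- ρ = 0.41: g = 0.705, variance 0.92 (0.92–0.93 in simulation), against 0.83 for proper covariate adjustment.
- ρ = 0.30: g = 0.65, variance 1.03, worse than no adjustment.

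With four rows and equal correlations, g = (1 + 3ρ)/4. The variances become 0.85 and 0.94, against 0.83 and 0.91. The loss is smaller but serves no purpose.

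**The case against.** The strongest defence is that the rule is not imbalance alone. The prognostic condition keeps irrelevant variables out of the primary model, and the plan speaks of examining baseline characteristics, not of significance tests, so the p<0.05 screen is only one reading. Both points stand, and they limit what the flag probabilities mean. They do not rescue balanced prognostic variables, which are still omitted.

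Second, T1 is already in the model, so baseline harms are not ignored. That is partly right: they inform the interaction. But the arms are not said to share a T1 mean. In a linear model with complete data and unrestricted arm-by-time terms, the T2 contrast is then simply the difference in T2 means, and T1 adds nothing to it.

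Third, Aim 2 is exploratory and puts effect sizes ahead of formal tests, and its shorter wording may abbreviate the general rule. This is fair. The mismatch invalidates neither aim; the two passages only need reconciling.

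A reader might infer more than the documents support:

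- That the rule inflates type I error or biases the estimate. A mechanical rule is nominal to conservative; the excess appears only if someone picks among versions.
- That power is lost for every contrast. It is not lost for the time-by-condition interaction.
- That the choice will be made by unblinded analysts. The documents do not say whether arm labels will be coded.

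**Conclusion.** The point holds in limited form. As written, the rule forgoes roughly three quarters of the precision that a prognostic covariate could give the T2 rate ratio, and it leaves the primary model undetermined until arm data are seen. The direction follows from the rule itself. The size does not: it rests on a linear approximation, 1:1 allocation, assumed correlations of 0.30 to 0.55 and an assumed p<0.05 cut-off. On that basis the choice is between a variance reduction of about 9–29% and one of about 2–9%.

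No definite number of power points can be claimed for this trial, because the documents give no effect size, event rate, dispersion or prognostic strength. Nor does the point show that 1,992 participants are too few. For Aim 2 the case is one of consistency and prespecification, because a covariate main effect does little for interactions with time. The change should be made, but the trial is valid without it.

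**What to change.** Delete the imbalance-driven rule from the general paragraph and from the Aim 2 paragraph. Before arm-level data are examined, name one short list of baseline covariates expected to be prognostic, used in both aims whatever the observed balance. Lifetime drinking (ever/never) and age are examples already collected through eligibility screening. The choice is the investigators', since the documents give no evidence on prognostic strength.

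State one use of baseline harms:

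- T1 harms as a covariate, with T2 to T4 as responses; or
- T1 kept as a response row, with the arm means constrained equal at T1, which randomisation after baseline justifies.

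Do not do both. Present baseline tables descriptively, without using them to select covariates, and label any imbalance-based adjustment as a sensitivity analysis.

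The cost is a few sentences of SAP text and a small rewrite of the primary model specification. No extra participants, visits or data are needed. The downside is that the covariate list can no longer be changed after arm data are seen.

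### The plan pre-specifies nothing for within-person overdispersion in the primary Poisson analysis of alcohol-related harms; if it is present, p-values are too small and intervals too narrow

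*Combined protocol and SAP*

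**What the plan says.** Statistical Considerations plans generalized linear mixed models "with a random effect for observations nested within persons and a link function dependent on the outcome distribution". For the primary outcome it then names the distribution: "Using a parallel two-group design, we will test whether the Poisson event rate ratio" of intervention to control "for alcohol-related harms reported at T2 (primary outcome) is different from 1". For change over time, "we will test the interaction term of time by condition", with time as four categorical occasions. The same section states: "Type I error will be set at 5% for all analyses". Aim 2 reuses similar models with three-way interactions.

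The section mentions no dispersion parameter, negative-binomial alternative, occasion-level random effect, robust standard error or dispersion check. The documents also do not give the harms instrument, its recall window, or an expected mean or variance.

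**The concern.** A person random intercept accounts for the fact that some participants always report more harms than others. Given the person, a Poisson model still sets the variance at each wave equal to the mean. A bad month, a change of friends, or harms that come in clusters would all be treated as pure Poisson noise.

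Such variation is plausible for 14–18-year-olds followed for 12 months. Having none would mean that each participant's underlying harm rate moves only by a factor common to everyone in the arm at that wave. If the variation is there and standard errors come from the model, the trial could declare the game effective more often than the stated 5% when it is not.

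**Working it through.** **Inputs from the documents.** 1,992 randomized; type I error 5%, treated as two-sided because the test is of a difference from 1; four occasions; Poisson rate ratio at T2; one person-level random effect. There is no planned figure to reproduce: no event rate, target rate ratio, power or dispersion is given.

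**Assumed inputs.** 1:1 allocation (996 per arm), no dropout, mean harms per wave m, person intercept normal on the log scale with SD σ, and an occasion-level gamma multiplier with mean 1 and variance k. The planned model corresponds to k = 0.

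**Step 1: the T2 time-by-condition term, by formula.** With complete data the person intercept cancels from this contrast. The model standard error is sqrt(1/S11 + 1/S12 + 1/S01 + 1/S02), where each S is the total harm count in one arm at T1 or T2. For m = 1 this is sqrt(4/996) = 0.063, whatever the value of k. The true variance is larger by the factor 1 + k·m·exp(σ²).

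- m = 1, σ = 1, k = 0.5: 1 + 0.5 × 2.718 = 2.36. The standard error is too small by √2.36 = 1.54, and the two-sided error is 2[1 − Φ(1.96/1.54)] ≈ 20%.
- m = 2, same σ and k: 1 + 0.5 × 2 × 2.718 = 3.72, factor 1.93, error about 31%.

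**Step 2: both tests, by simulation under no effect.** There were 3,000 trials per scenario. Each was fitted with the planned model (Poisson, person intercept, time, arm, time by arm; adaptive quadrature; model-based standard errors) and re-tested with participant-clustered robust standard errors. Monte Carlo error is about 0.4 points near 5% and up to 0.9 at the highest rates. Rejection rates (%) at nominal 5%:

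| m | σ | k | T2 rate ratio, model SE | T2 interaction, model SE | T2 rate ratio, robust SE | T2 interaction, robust SE |
|---|---|---|---|---|---|---|
| 1 | 1 | 0 | 4.5 | 5.2 | 4.6 | 5.3 |
| 1 | 1 | 0.25 | 7.8 | 12.0 | 5.6 | 4.8 |
| 1 | 1 | 0.5 | 10.0 | 18.1 | 4.4 | 5.4 |
| 1 | 1 | 1 | 13.7 | 30.6 | 4.4 | 5.8 |
| 2 | 1 | 0 | 5.0 | 5.1 | 5.1 | 5.3 |
| 2 | 1 | 0.25 | 8.9 | 21.1 | 4.9 | 5.4 |
| 2 | 1 | 0.5 | 11.9 | 29.9 | 4.9 | 5.4 |
| 2 | 1 | 1 | 16.1 | 42.4 | 4.8 | 5.0 |
| 0.5 | 1.5 | 0 | 5.8 | 4.9 | 5.8 | 5.2 |
| 0.5 | 1.5 | 0.5 | 10.8 | 24.5 | 5.0 | 5.4 |
| 0.5 | 1.5 | 1 | 16.8 | 36.5 | 5.3 | 5.8 |

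At m = 1, k = 0.5 the model standard error for the T2 log rate ratio is 0.069 against a true 0.082; for the interaction it is 0.064 against 0.095. The rate ratio suffers less because most of its variance is between persons, which the random intercept does capture.

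**Step 3: zeros.** Eligibility Criteria admits youth who "have drank alcohol in their lifetime or intend to in the next year", so many zero counts are likely. With 30% of participants at zero on every wave and k = 0, the interaction rejected 5.0% in one run (m = 0.5) and 5.7% in another. Adding k = 0.5 at m = 0.5 gave 16.0%. The Step 1 formula gives the same from dispersion alone: the mean among the other 70% is 0.5/0.7 = 0.714, the factor is 1 + 0.5 × 0.714 × 2.718 = 1.97, and the error is about 16.3%. Starting to drink during follow-up is a different matter, since it is within-person change. With 30–50% baseline non-drinkers, assumed onset times and no other dispersion, rejection was 5–12% for the interaction and 6–7% for the rate ratio.

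**The case against.** The best defence is that this is silence, not a stated error. The plan never says its standard errors are model-based, and both a robust Poisson and a log-link negative-binomial analysis would still estimate a rate ratio. It also lets the link depend on the outcome distribution. The first part stands: the fault is a missing specification. The second gives little protection. A link is not a variance function, Poisson and negative binomial commonly share the log link, Poisson is named for this outcome, and no rule for leaving it is given.

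The size is also open to challenge, and this stands too. At k = 0.1 the interaction rejected only 7.4% (m = 1) or 6.3% (m = 0.5). The direction depends on the instrument: a score summing 10 independent yes/no items with a stable personal propensity (assumed mean about 1.5) rejected 2.1%, which is conservative.

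Three stronger readings may tempt a reader:

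- **That the 5% level is certainly lost.** The documents give no harm distribution, and at k = 0 the plan keeps its level.
- **That the never-drinkers admitted at entry break the model.** Persistent zeros alone do not (Step 3).
- **That the 12–42% range applies to the primary outcome.** The plan attaches the primary label to the T2 rate ratio, for which the range on the same grid is 8–16%.

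For Aim 2, the plan puts effect sizes ahead of formal testing, so false positives matter less there. It still interprets a significant three-way interaction, and its intervals would be affected in the same way.

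**Conclusion.** The concern holds conditionally. The primary count model makes no provision for extra-Poisson variation within a person across waves. If that variation exists and model-based standard errors are used, the nominal 5% becomes about 8–16% for the primary T2 rate ratio and about 12–42% for the T2 time-by-condition term. Those ranges rest on assumed values: m of 1–2, σ = 1, k of 0.25–1, equal arms and no dropout. With k = 0 the planned tests are sound (about 4.5–5.8%). The mechanism follows from the model as written; how large the effect will be in this trial cannot be determined from the documents.

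**What to change.** Keep the Poisson mean model and the rate ratio. State in Statistical Considerations that every test and confidence interval on the harm count, including the time-by-condition tests and the Aim 2 count models, uses participant-clustered robust (sandwich) standard errors. For the primary outcome, remove the dependence on the observed distribution, so that no choice is left until the data are seen. A negative-binomial mixed model can be named as a sensitivity analysis; its error rates were not examined here, which is why it is not the first choice.

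The cost is a sentence or two of text and one software option. Intervals widen when overdispersion is present: by 0.082/0.069, about 19%, for the T2 log rate ratio at m = 1, k = 0.5. When it is absent they barely change (robust and model standard errors were both 0.066 at m = 1, k = 0).

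### The T2 rate ratio rests on an unstated missing-at-random assumption: the covariate rule tends to leave out predictors of dropout, and no sensitivity analysis tests it

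*Combined protocol and SAP*

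**What the plan says.** Under Study Design & Methods: "This study is a randomized controlled trial with SGMY (n=1,992) who are recruited via social media from across the United States". The timing of allocation and the survey schedule follow: "Participants will be randomized after baseline to the Intervention or Control condition"; "We will conduct surveys with SGMY at baseline, 3-, 6-, and 12-month follow-up". T2 is taken to be the 3-month survey from the order of the waves.

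Under Statistical Considerations, the model is: "Our primary analyses will use generalized linear mixed models (i.e., multilevel repeated-measures models) with a random effect for observations nested within persons". Time is categorical over T1 to T4, so baseline harms appear to be fitted as an outcome. The primary test is whether the Poisson rate ratio "for alcohol-related harms reported at T2 (primary outcome) is different from 1". The analysis set is described as: "We will conduct our primary analyses as intent-to-treat, wherein all participants are included according to the condition they were randomized to".

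The only covariate rule for the Aim 1 model is: "We will control for variables (potential confounders) that differ meaningfully across study arms and are prognostic with the outcome".

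The supplied text gives no expected attrition, missing-data assumption, imputation, report of loss by arm, or sensitivity analysis for missing T2 harms. The intensity-adjusted analysis is mentioned only for Aim 2 and concerns exposure to the intervention, not missing outcomes.

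**The concern.** The primary outcome is a self-reported count from a web survey of teenagers recruited on social media, so some loss before T2 is likely. A participant who never returns after baseline contributes one T1 count. The mixed model then predicts that person's T2 from arm, the T1 count and whatever covariates are fitted. This is sound only if, within arm, loss is unrelated to T2 harms once those quantities are known.

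Two features of the plan leave this exposed. First, a covariate must differ between arms and be prognostic to be fitted. Randomisation balances most baseline variables, so a variable that predicts both dropout and later harms will usually stay out of the model even though the trial holds it. The minority-stress measures needed for Aim 2 are an example: the background section itself treats them as drivers of drinking. Second, nothing tests what happens if the assumption fails. The arms play games on different subjects, alcohol and coping in one and nutrition in the other, so reasons for leaving could differ by arm. A shift in the ratio from this source would be reported as an intent-to-treat result with nothing to show how far it depends on those who left.

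**Working it through.** **Inputs from the documents.** N = 1,992; randomisation after baseline; four waves; Poisson rate ratio at T2; mixed model with a person-level random effect; Type I error 5%. The plan gives no power, target ratio, event rate, allocation ratio or attrition, so there is no figure of its own to reproduce here. Everything below rests on assumed rates.

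**Simulated data.** True T2 ratio 1. Counts are Poisson with log-rate −0.5 + 0.5X + u at T1 and a further gX at T2, where u ~ N(0,1) and X is a baseline marker present in 30%. There are 120,000 participants per scenario.

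**Fitted model.** Log-rate = b0 + b1·arm + b2·T2 + b3·arm·T2 + person intercept, by maximum likelihood with 25-point Gauss-Hermite quadrature. The T2 ratio is exp(b1 + b3).

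**Marker-driven loss.** Control loss is 20%. Intervention loss is 15% without X and 40% with X, in total 0.7 × 15% + 0.3 × 40% = 22.5%.

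**Count-driven loss.** Control loss is 20%. Intervention loss is 40% with 3 or more harms and 15% otherwise. When the T2 count drives it, total loss is about 20% in both arms.

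| What drives loss in the intervention arm | Estimated T2 ratio (truth 1) |
|---|---|
| Nothing (completely random, 20%) | 0.98 to 1.00 |
| T1 harms (40% if 3 or more, otherwise 15%) | 0.988 (g = 0.5), 0.998 (g = 0) |
| X, omitted, g = 0.5 | 0.940 |
| X, omitted, g = 0.3 | 0.954 |
| X, omitted, g = 0 | 0.99 to 1.00 |
| X, fitted with its time term (g = 0.5; g = 0.3) | 0.993; 0.996 |
| T2 count | 0.896; repeat runs 0.91 to 0.94 |
| T2 count, X fitted with its time term | 0.908 |

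Simulation noise is about 0.01 to 0.02.

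**At the trial's own size.** This used 80 simulated trials of 1,992 with 1:1 allocation, T1 and T2 only, and no marker.
- Loss of 30% versus 10% unrelated to outcome gave 0.996.
- Loss of 26% versus 10% driven by T1 harms gave 1.005 from the mixed model, but 0.83 from a comparison of T2 responders alone.
- Loss of 26% versus 10% driven by T2 harms gave 0.797 from the mixed model. This is a harsher case than those in the table.

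**Adding T3 and T4.** If nobody lost before T2 returns, the marker scenario (g = 0.5) gives 0.939 to 0.942 and the T2-count scenario 0.916, so the later waves do not rescue the contrast. If half of the T2 non-responders return at each later wave, the figures are 0.963 and 0.927, against 0.953 and 0.902 with two waves in the same set of runs.

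**Scale.** An approximate standard error of the log ratio is √[(1/μ + k)·2/n], with n = 996 × 0.8 = 796.8 per arm.
- μ = 2, k = 0: √(0.5 × 2/796.8) = 0.035.
- μ = 0.5, k = 3: √(5 × 2/796.8) = 0.112.
- A ratio of 0.94 is a log shift of 0.062, and 0.90 is 0.105. The shift is therefore between 0.062/0.112 ≈ 0.6 and 0.105/0.035 = 3.0 standard errors.
- The ratio detectable with 80% power under the same assumptions runs from 0.73 to 0.91.

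**The case against.** The strongest reply is that the planned model already does most of the work. Everyone randomised has T1 data, the likelihood uses all available waves, and those who miss only T2 may still supply T3 or T4. A reader might infer that the intent-to-treat statement is false. The documents do not support that: on the repeated-measures reading, all participants can be analysed as randomised. It would fail only if T2 were compared among T2 responders alone, and the text does not say that.

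A reader might also infer that unequal loss by itself biases the result, or that heavier drinkers leaving one arm must do so. Neither follows. Loss of 30% versus 10% unrelated to outcome leaves the ratio at 1, and drinking that shows in T1 harms is handled by the model.

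The marker scenario needs the marker's effect to grow between T1 and T2. With a constant effect almost nothing is left. Even at 0.94 to 0.95 the bias is smaller than the effects the trial could detect under the assumed rates. Returning participants soften it further. All loss rates, event rates and dispersion values are assumed.

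These points narrow the concern but do not remove it. None supplies a stated assumption or a check, and none covers loss related to T2 harms beyond what T1 harms reveal.

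**Conclusion.** The concern holds in a limited form. The T2 ratio depends on a missing-at-random assumption that the plan does not state, weakens through its covariate rule, and does not test. Bias arises when loss in one arm relates to T2 harms beyond T1 harms. With assumed loss near 20% per arm and a true ratio of 1, it moves the estimate to about 0.90 to 0.94 if loss depends on T2 harms, and to about 0.94 to 0.95 if it depends on an omitted marker of growing effect. It is close to nil if the marker's effect is constant. The opposite pattern of loss would hide a benefit.

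Fitting the marker with its time term cures the marker scenario but barely moves the T2-dependent one (0.896 to 0.908), so better covariates and a sensitivity analysis are both needed. That second scenario also has near-equal total loss, so comparing attrition by arm would not reveal it. This is an improvement the plan should make before outcome data are seen. It is not a reason to abandon the primary model.

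**What to change.** All three changes are to Statistical Considerations.

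1. Replace the imbalance-based covariate rule with a fixed set of prognostic baseline variables that the trial collects. Age and the minority-stress measures are examples, plus baseline drinking if it is collected. Enter them with their time terms, or use them as auxiliary variables in multiple imputation, whether or not they differ between arms.
2. Keep the T2 rate ratio as primary. State that it comes from the repeated-measures model and assumes data missing at random given that model. Report T2 loss by arm.
3. Pre-specify one delta-adjusted tipping-point analysis. It should vary the assumed T2 harm rate of non-responders separately in each arm and report where the conclusion changes.

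The cost is SAP wording and some extra analysis, with no new data, visits or participants. The interval may be slightly wider under imputation, and the tipping-point result may make the conclusion look less firm.
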